8.3 Covariate adjustment

The main analysis of the primary outcome will be a covariate adjusted proportional odds model.

Covariates that will be adjusted for include

- Race/ethnicity defined as a single categorical variable for non-Hispanic White/Caucasian, non-Hispanic Black/African American, Hispanic, Other.
- Age as a continuous variable in years; modeling will assess for linear effect or cubic splines based on the study data.
- Gender as a categorical variable for male, female, undifferentiated, and no answer
- Duration of acute respiratory infection symptoms prior to study drug receipt in days calculated as the duration reported at enrollment for randomization plus the additional days

until receipt of study drug

- Presence of comorbidities as a dichotomous variable for presence of any or absence of all of the following: hypertension, diabetes mellitus, obesity, chronic kidney disease, chronic cardiopulmonary conditions, or immunosuppressive conditions.
- Monoclonal antibodies taken for the treatment of COVID-19 prior to randomization defined as a binary variable (yes/no)
- SARS-CoV-2 vaccinations were added to the data collection on May 14th, 2021. After that time, enrolled subjects will be categorized as fully vaccinated (at least 14 days after 2nd dose of SARS-CoV-2 mRNA vaccine or after single dose of J&J vaccine prior to randomization); partially vaccinated (receipt of one or more doses of SARS-CoV-2 vaccine but not fully vaccinated prior to randomization); and not vaccinated. Between December 14th, 2020 (first day of public vaccination in the US under EUA) and May 13th, 2021, vaccination status will be recorded as missing. Prior to December 14th, 2020, vaccination status will be recorded as not vaccinated.
- Time period when date of randomization occurred defined as a categorical variable in quarters (3 month) periods beginning with June 2020-August 2020, September 2020-November 2020, December 2020-February 2021, etc.

Center effects will be accounted for with the specification of a random intercept. The defined groupings above may be modified to collapse groups pending the available data at time of final study analysis.

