## 6.1 Baseline Variable Collection

- Informed Consent Document and documentation of consent process
- Presence or absence of each inclusion and exclusion criterion
- Date and time of enrollment
- Day of symptom onset
- Specimen type, date, and result of SARS-CoV-2 testing conducted clinically.
- Demographics (age, sex, race, ethnicity, height, weight)
- Comorbidities: chronic cardiac disease, chronic pulmonary disease, chronic kidney disease, chronic liver disease, chronic neurological disease, malignant neoplasm, chronic hematologic disease, AIDS/HIV, obesity, diabetes with complications, diabetes without complications, rheumatologic disorder, malnutrition, smoking, other
- Chronic use of medication: ACE inhibitors, angiotensin receptor blockers
- Receipt of azithromycin in the past week
- Presenting signs and symptoms, along with self-reported severity

## 6.2 Daily Assessments between Randomization and Study Day 16, and then at Day 29

- Study drug administration and reason for missed doses.
- Modified COVID Ordinal Outcomes Scale
- Daily signs and symptoms, along with self-reported severity via electronic log and/or telephone interview.
- Day of symptom resolution
- Receipt of open label antivirals: chloroquine, hydroxychloroquine, remdesivir, lopinavir/ritonavir, other
- Receipt of open label immunomodulators between enrollment and hospital discharge: corticosteroids, tocilizumab, sarilumab, interferon  $\beta$ , other
- Receipt of azithromycin
- Study days in hospital (if applicable)
- Study days receiving supplemental oxygen (if applicable)
- Study days receiving non-invasive or invasive mechanical ventilation (if applicable)
- Study days in ICU to Study Day 29
- Study day of death (if applicable)
- Safety Outcomes: seizure, atrial or ventricular arrhythmia, cardiomyopathy, cardiac arrest, aspartate aminotransferase or alanine aminotransferase levels that are greater than twice the local upper limit of normal (or two times higher than known baseline), acute pancreatitis (defined by a clinically obtained lipase level above the local upper limit of normal and abdominal pain or vomiting), stage II or greater acute kidney injury according to KDIGO criteria, receipt of new renal replacement

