4.1 Preface

Effective therapies for COVID-19 are urgently needed. Lopinavir/ritonavir (Kaletra), an antimicrobial agent used to treat HIV-1, has demonstrated in vitro inhibition of SARS-CoV-2, the virus that causes COVID-19. Initial clinical data have suggested possible relevance as a therapeutic agent when administered early in the disease course of patients with COVID-19. The TREAT NOW study was designed to test the hypothesis that lopinavir/ritonavir reduces disease progression and improves clinical status measured using a seven point at day 15 following receipt of study drug when compared with placebo. The TREAT NOW study is a multicenter, blinded, non-matching placebo-controlled, randomized clinical trial to evaluate the superiority of active therapy (lopinavir/ritonavir) versus placebo control. Briefly, patients testing positive for SARS-CoV-2 infection in an outpatient setting are contacted by research coordinators and invited to participate. Adults with a positive SARS-CoV-2 test are either self-referred or identified via review of testing records at participating sites. Patients who are still symptomatic and who are within six days of symptom onset are invited to participate. Eligible participants who provide their consent to participate using an electronic system undergo comprehensive baseline data collection via phone survey, the participant is randomized, and study drug or placebo is shipped overnight to the participant's home. The participant then completes a daily web-based medication adherence, symptom burden, and hospitalization survey for sixteen days. Missed surveys result in telephone follow up to complete missing data and to re-engage the participant in completing the study. At day 15, the primary outcome is assessed. Patients are followed up once more at 29 days

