9.1 Descriptive analysis

Using data pooled across all sites, the study sample will be characterized based on demographic and clinical variables measured at randomization, unless otherwise indicated. Specifically, the following variables will be described:

1. Age (years)
2. Sex (male, female, undifferentiated, no response)
3. Race (Black/African American, White/Caucasian, American Indian/Alaskan Native, Asian, Native Hawaiian/Other Pacific Islander, other, no answer)
4. Ethnicity (Hispanic, non-Hispanic)
5. Race/ethnicity (non-Hispanic Black/African American, non-Hispanic White/Caucasian, Hispanic, other)
6. Body mass index (kg/m²)
7. Presence of comorbidities (yes/no):
 - a. chronic cardiac disease
 - b. chronic pulmonary disease
 - c. chronic kidney disease
 - d. chronic liver disease
 - e. chronic neurological disease
 - f. malignant neoplasm
 - g. chronic hematologic disease
 - h. AIDS/HIV
 - i. obesity
 - j. diabetes with complications
 - k. diabetes without complications
 - l. rheumatologic disorder
 - m. malnutrition
 - n. immunosuppressive conditions
8. Tobacco product use (current, former, never)
9. E-cigarette or vaping product use (current, former, never)
10. Chronic use of medication (yes/no):
 - a. ACE inhibitors
 - b. angiotensin receptor blockers
11. Receipt of azithromycin in the past week
12. Presence of symptoms (yes/no):
 - a. Cough
 - b. Fever
 - c. Shortness of breath
 - d. Chest pain
 - e. Abdominal pain

- f. Nausea
- g. Diarrhea
- h. Body aches
- i. Weakness/fatigue

13. Total number of symptoms reported (count)

14. Symptom duration (days)

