10.1 Primary Efficacy Analysis

The primary outcome of the Modified COVID Ordinal Outcomes Scale from Study Day 1 through Study Day 15 will be evaluated in the ITT dataset using a Bayesian longitudinal proportional odds model. The model will include a random intercept for each participant to account for the repeated measurements over time to calculate the posterior probability that a treatment arm compared to the placebo-controlled arm has an $OR > 1$, suggesting any benefit for the treatment. The proportional odds assumption will be examined using graphical methods—e. g., the logit of the empirical cumulative distribution function of the ordinal scale should be parallel among categories of

covariates. If proportionality is clearly violated, we will consider partial proportional odds or non-proportional odds models.

The model will be adjusted for the variables described in Section 8.3. To account for changes in the effect size between treatment groups from Study Day 1 to Study Day 15, an interaction between randomized group and time will be included. Time will initially be modeled using a cubic spline, but it may be modified to a simpler or more complex representation of time if needed to appropriately model the effect over time.

The prior for the intercept for the proportional odds regression model will assume a Dirichlet distribution. The treatment effect, as defined as a log odds ratio in the model, will have a normal prior defined so that $P(OR > 1) = P(OR < 1) = 0.5$ (i.e., equally as harmful as beneficial) and $P(OR > 2) = P(OR < \frac{1}{2}) = 0.025$ (i.e., large effects in either direction unlikely), with the variance computed to satisfy these criteria. For all other covariates the prior distributions will be normal with mean 0 and a larger variance to reflect the uncertainty of their potential effect.

The convergence of the Markov chain Monte Carlo simulations will be checked via diagnostics, with alternative priors, models, and chain lengths/burn-ins explored if necessary to achieve convergence and satisfy any model assumptions.

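### The primary model leaves out the baseline symptom count, which is already collected; adding it could recover a little precision at almost no cost

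*SAP*

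**What the plan says.** SAP 8.3 opens with "The main analysis of the primary outcome will be a covariate adjusted proportional odds model" and lists eight covariates: race/ethnicity, age, gender, symptom duration up to drug receipt, any comorbidity, prior monoclonal antibodies, vaccination status and calendar quarter. Center enters as a random intercept. SAP 10.1 adopts the list: "The model will be adjusted for the variables described in Section 8.3". The same section adds that "The model will include a random intercept for each participant to account for the repeated measurements over time", and that "an interaction between randomized group and time will be included".

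The symptom count is a pre-treatment variable in these documents. Protocol 6.1 has among its baseline items "Presenting signs and symptoms, along with self-reported severity". SAP 4.1 gives the order of events: eligible, consenting participants "undergo comprehensive baseline data collection via phone survey, the participant is randomized". SAP 9.1 describes the sample by "demographic and clinical variables measured at randomization, unless otherwise indicated"; item 12 of that list names nine symptoms and item 13 is their total number. The count appears nowhere in SAP 8.3, and the protocol's shorter covariate list (Section 7: age, gender, symptom duration) does not contain it either.

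**The concern.** The primary outcome is largely a symptom scale. Levels 5, 6 and 7 differ only by symptoms and limitation in activity, and the example table in SAP Section 7 puts 10% + 24% + 55% = 89% of placebo patients there. The natural covariate for such an outcome is the baseline level of the thing measured, and the model has no baseline term for symptom burden. The count is the closest summary that the SAP already names.

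If the count predicts Day 1 to 15 status beyond the eight covariates, the between-participant variance is larger than it need be and the treatment odds ratio is estimated less precisely than the collected data allow. Validity is not at stake. In a randomized comparison, omitting a pre-treatment variable neither confounds the effect nor inflates the type I error.

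**Working it through.** **The plan's own figure.** SAP Section 7 gives 540 patients for 90% power at an odds ratio of 1.75, type I error 0.05, by Whitehead's method. The mean of the two arms in the table is 0.8, 2.4, 3.2, 2.45, 8.3, 21.35 and 61.55%. The sum of cubes is about 0.2435 (0.6155³ = 0.2332, 0.2135³ = 0.0097, 0.083³ = 0.0006, the rest negligible). Two-sided:

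N = 12(z_α + z_β)² / [ln(OR)² (1 − Σp̄³)] = 12 × 10.507 / (0.3132 × 0.7565) = 532.

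This is within 2% of 540, and 540/0.9 = 600. (The SAP does not state sidedness; one-sided gives 434.) The formula contains no covariates, so the omission does not touch it. Power at 540 is Φ(√(540 × 0.2369/12) − 1.96) = Φ(1.305) = 90.4%.

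**Rough scale of the gain.** If the count explains a share R² of the residual variance, the effective sample size is N/(1 − R²). The documents give no R². For assumed values of 0.01, 0.02, 0.05 and 0.10 the effective N is 545, 551, 568 and 600, and power rises from 90.4% to 90.7%, 91.0%, 91.8% and 93.1%.

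**Random-intercept model, simple version.** Setting: N = 540, 15 days, four levels, constant log odds ratio 0.560, participant-intercept SD 2, maximum likelihood, 150 runs.

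- Covariate explaining 4% of the intercept variance: mean estimate 0.572 without and with it; model SE ratio 0.984.
- Covariate explaining 10%: mean estimate 0.570 without and with it; SE ratio 0.957.

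With 1:1 allocation the squared SE is about 4V/N, so V = 0.1817² × 540/4 = 4.46. Removing 0.4² = 0.16 gives √(4.30/4.46) = 0.982. For the second case V = 0.1815² × 540/4 = 4.45, and removing 0.63² = 0.397 gives √(4.05/4.45) = 0.954. Both agree with the simulated ratios. The spread of the 150 estimates did not itself fall (0.195 to 0.198; 0.191 to 0.193). A gain this small is not resolved by that many runs, so the support comes from the model SEs and the formula. The run does show that the estimate does not shift.

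**Random-intercept model with treatment-by-time term.** Assumptions: nine yes/no symptoms with prevalences 15% to 75% and latent correlation 0.3 (count mean 4.1, SD 2.0). One composite score stands for the eight covariates (odds ratio 1.5 per SD, correlation 0.22 with the count) and is in every fit. Four levels; Days 1, 3, …, 15; effect zero on Day 1 rising linearly to 68.1% in level 7 on Day 15; intercept SD 2; 800 trials per scenario. In case A the count is itself the predictor. In case B an unmeasured burden is, and the count is its proxy (correlation 0.78). SAP 10.1 does not say which contrast yields the tested odds ratio, so several are shown. Efficiency gain is the squared ratio of mean z, with over without the count, minus 1.

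| Case, OR per SD | Day 15 SE, without → with | Efficiency gain | Day 1–15 average, power | Efficiency gain |
|---|---|---|---|---|
| A, 1.25 | 0.218 → 0.215 | 2% | 72.8% → 73.9% | 3% |
| A, 1.5 | 0.223 → 0.216 | 6% | 72.3% → 75.6% | 8% |
| A, 2 | 0.237 → 0.218 | 18% | 70.4% → 79.5% | 24% |
| B, 1.25 | 0.217 → 0.216 | 1% | 72.9% → 73.6% | 2% |
| B, 1.5 | 0.222 → 0.218 | 3% | 72.7% → 74.4% | 4% |
| B, 2 | 0.234 → 0.224 | 8% | 72.0% → 76.5% | 11% |

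Power on the Day 15 contrast is already about 99% (case A: 99.3% to 99.4%, 99.3% to 99.5%, 99.2% to 99.7%). For the treatment-by-time coefficient alone the efficiency gain is 0.2% or less. With no association, no contrast changes.

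**Single-day model (Day 15 scale, a secondary outcome in SAP 5.3).** Here adjustment works differently: in case A at odds ratio 2 the SE rises from 0.178 to 0.183 while the odds ratio moves from 1.83 to 1.94. Power goes from 91.6% to 91.8%, 91.8% to 92.8% and 93.1% to 96.2% in case A, and from 91.6% to 91.7% with no association. In a separate 1,500-run check of the single-day model, type I error with the covariate omitted was 5.2% to 5.4%.

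**The case against.** The strongest reply is that no defect exists. The eight covariates are prespecified, already extend the protocol's three, and come with participant and center random intercepts. Nothing in the documents promises adjustment for symptom burden, and the same could be said of other items described in SAP 9.1, such as smoking. This stands as a statement of status: the point is an optional refinement.

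The larger gains also rest on a generous assumption. An odds ratio of 2 per SD for the count, against 1.5 for the composite of all eight covariates, gives the count (ln 2 / ln 1.5)² = 2.9 times their prognostic variance. At 1.5 it equals them; only at 1.25 is it weaker, and there almost nothing is gained. This also stands, and the rows for 2 should carry little weight. The visible power gains arise only on the Day 1–15 average, which the SAP does not name as its contrast and whose roughly 72% starting power reflects the assumed zero effect on Day 1. The single-day shift is non-collapsibility of the odds ratio, not a precision gain.

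Finally, SAP 8.3 mentions a data-collection change of May 2021, and efficacy looks begin after at least 200 participants (SAP 8.5.2). Any look already made used the model without the count. That is the real cost. It calls for disclosure but does not make the change unsound.

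**Conclusion.** The point holds as a conditional, optional improvement. The primary model omits a baseline variable that is already collected and plausibly prognostic for a symptom-driven outcome. No bias follows, and the sample size and stated power stand.

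On the planned structure, the Day 15 standard error would fall by about 1% to 3% if the count carries an odds ratio of 1.25 to 1.5 per SD in its own right, and by about half that if it is a proxy. It would fall by 8% only at an odds ratio of 2. If the count predicts nothing, the simulations show no loss.

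These sizes depend on assumed associations, prevalences, intercept variance and effect trajectory. The skeptical prior, spline time, center effect, missing days and death as an absorbing state were not modelled, so the actual Bayesian analysis may differ. Confidence in the size is moderate.

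**What to change.** Before unblinding:

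- In SAP 8.3, add the total symptom count (SAP 9.1, item 13) as a continuous covariate of the primary model. Name the symptoms counted; item 12 lists nine.
- State that it comes from the pre-randomization baseline form, not the Study Day 1 survey. Protocol 9.1.2 lists diarrhea, nausea, abdominal pain and fatigue as reactions to the study drug, and these are among the counted symptoms, so a count taken after the first dose could be affected by treatment.
- In SAP 8.4, add the count to the enrollment covariates that are imputed if missing.
- In SAP 10.1, say that the reported odds ratio is conditional on the count, and note any efficacy or futility look already made without it.

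The cost is one model term and a few sentences, with no new data. The secondary models need not change. If the term is wanted there, SAP 10.2.1, which names no adjustment covariates, must be edited too. If the sponsor prefers the present list, a sentence recording why the count was left out would be enough.

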8.4 Missing Data

Missing outcome data for an analysis population will be imputed when necessary using multiple imputation. Outcomes using the Bayesian longitudinal proportional odds model, which includes the primary outcome, will not use imputation since the model facilitates smoothing over missing responses (i.e., the model can still be used even if a participant has missing day(s) of response data). Data on age, gender, race/ethnicity, comorbidities, and duration of acute respiratory infection prior to randomization should not be missing as they are collected as part of enrollment, however imputation procedures will be used in cases of missing values.

8.5 Interim Analyses and Data Monitoring

8.5.1 Purpose of Interim Analyses

Interim analyses are planned for safety, efficacy, and futility. The results of the interim analyses will be reported to the DSMB, along with the stopping guidelines described in this Statistical Analysis Plan. The DSMB may request additional interim analyses. Such requests will be fulfilled by the unblinded statistician and will not be reported outside of the DSMB meeting.

8.5.2 Planned Schedule of Interim Analyses

The first interim analysis is planned after at least the first 50 participants have been enrolled and achieved follow-up through at least Study Day 15. This first analysis will present only safety data to the DSMB. The second and subsequent interim analyses will include both safety and efficacy data, and are planned to occur after at least 200 participants have been enrolled and have their primary outcome observed at Study Day 15. Futility interim analyses will begin after approximately 400 participants have been observed and will be conducted in addition to interim analyses for safety and efficacy.

This trial is planned to be analyzed using a Bayesian approach, and so a strict interim analysis schedule is not prespecified. Instead, the schedule for subsequent interim analyses will be decided by the DSMB based upon the rate of accrual, the safety and feasibility data from at least the first 200

participants, opportunities to add new agents, and other relevant considerations.

8.5.3 Adaptations

The statistical design of this study is sufficiently flexible to allow for future adaptations. However, no adaptations are currently planned. Should new agents become available for inclusion in the study, or should there be sufficient evidence to warrant changes in the planned randomization allocation probabilities or sample size, the adaptations will be encoded in a revision to this document before being implemented.

8.5.4 Stopping Rules

Given the Bayesian nature of the analysis, the *posterior probability* of the odds ratio for the primary outcome exceeding certain thresholds will be used to guide decisions to stop the trial early for efficacy or harm. These are:

Probability	Evidence For	Action Trigger
$P_1 = P(\text{OR} > 1 \mid \text{data})$	Any benefit	$P_1 > 0.95$
$P_2 = P(\text{OR} < 1 \mid \text{data})$	Inefficacy or potential harm	$P_2 > 0.90$

The criteria for P_1 represents scenarios where an intervention arm would stop early for efficacy, whereas P_2 represents early termination of an intervention arm for inefficacy or potential harm.

Interim monitoring for futility will be based on the *posterior predictive probability* that $P(\text{concluding efficacy at } N=300 \text{ per group} \mid \text{interim data})$. For the calculation of PPoS, the efficacy threshold on study completion will be based on the posterior probability that $P(\text{OR} > 1 \mid \text{data}) > 0.90$. The posterior predictive probability of success (PPoS) will be estimated via upstrapping the remaining number of participants to be enrolled from participants who have completed through Study Day 15 regardless of level of missing data (Crainiceanu and Crainiceanu 2020). The PPoS will be based on 1,000 upstraps of the “completed” trial with stopping rules based on the following table:

Predictive Probability of Success (PPoS) Action Trigger	Action
$\text{PPoS} < 0.10$	Stop for futility
$0.10 \leq \text{PPoS} < 0.25$	Consider stopping for futility based on trial characteristics (e.g., accrual), secondary endpoints, and external factors
$\text{PPoS} \geq 0.25$	Continue trial

8.5.5 Considerations for Multiplicity of Testing

Unlike a frequentist design with confidence intervals and p-values relating to the unknown parameters, a Bayesian design conditions on the data to estimate the unknown parameters. Therefore, the type of control for multiplicity used in a frequentist approach is inappropriate. However, it is not uncommon to attempt to understand the frequentist operating characteristics for Bayesian designs. We note that a 5% type I error rate with identical assumptions to detect an OR=1.75 achieves 86.4% power with a target sample size of 600. With regards to repeated evaluations of efficacy using the Bayesian approach, the posterior probability is an estimate of the unknown parameter conditional on the data collected thus far and any prior estimates of the posterior probability are irrelevant, and so multiplicity adjustments are not warranted and would be inappropriate.

9 Summary of Study Data

All continuous variables will be summarized using the following descriptive statistics: n (non-missing sample size), mean, standard deviation, median, minimum, 1st quartile, 3rd quartile, and maximum. All categorical variables will be reported as the frequency and percentages of observed levels with a clear definition of the denominator. In general, summary tables will be based on the relevant population (e.g., ITT, safety) and structured with a column for each study arm and will be annotated with the total sample size relevant to that table/treatment, including the number of missing observations.

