6.3 Randomization and Blinding

Eligible patients will be randomized in a 1:1 ratio to the intervention arm (lopinavir/ritonavir) or the control arm (placebo). Randomization is stratified by site and age (≥ 65 years versus < 65 years) and uses permuted small block randomization. Patients, treating clinicians, trial personnel, and outcome assessors are blinded to group assignment. Only the investigational pharmacy (who is distributing study medication), the Data Coordinating Center (who is managing the randomization systems including generating the randomization sequence), and one member of the statistical team (who is preparing closed DSMB interim reports) are unblinded.

To maintain the blind, study medication is dispensed with packaging and labelling that does not indicate whether the drug is a placebo or active treatment. Unblinding will occur only if required for subject safety or treatment at the request of the treating clinician and will be done by the

Investigational Pharmacy.

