6.4 Timing of study procedures and outcomes assessments

The day of randomization is defined as Baseline and the receipt of the study drug is defined as “Study Day 1”. It is possible for it to take up to two days for study medications to arrive at a participant’s home. For the purposes of analysis, Study Day 1 will be counted as the day on which study medications are received by the participant. To ensure symptoms are assessed daily while on study, and to ensure the primary outcome can be measured through Study Day 15, symptoms are collected daily from the day following randomization to sixteen days following randomization. The symptoms assessed on Study Day 1 (day of receipt of medication) to Study Day 15 are included in the measurements for this trial. At Study Day 15, the primary outcome is assessed. At Study Day 29, additional outcomes are assessed.

7 Sample Size

This study is designed to be analyzed using a Bayesian approach, accepting the possibility of adaptations or sample size adjustments as the trial progresses. Although the design as detailed is Bayesian in nature, a frequentist sample size and target power are provided for consistency with FDA guidance and recommendations. To provide a sample size estimate, we calculated a sample size of 540 patients equally distributed among study arms is needed to have 90% power to detect an odds ratio of 1.75 or greater assuming a traditional proportional odds model and a type I error of 0.05, as proposed by Whitehead (1993). Accounting for an approximate 10% loss to follow-up rate, we plan to enroll 600 patients

An example of the difference between study arms resulting in such an odds ratio is shown in the table. This is based on recommendations from the World Health Organization for COVID-19 Master Protocols that were in place at the time this study was designed

Category	Placebo Arm Proportion	Treatment Arm Proportion
1-Death	1%	0.6%
2-Hospitalized on mechanical ventilation or ECMO	3%	1.8%
3-Hospitalized on supplemental oxygen	4%	2.4%
4-Hospitalized not on supplemental oxygen	3%	1.9%
5-Not hospitalized with symptoms and limitation in activity	10%	6.6%
6-Not hospitalized with symptoms but with no limitation in activity	24%	18.7%
7-Not hospitalized without symptoms nor limitation in activity	55%	68.1%

8 General Analysis Considerations

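### SAP 8.5.5 quotes a 5% type I error that does not describe the efficacy rule in 8.5.2 and 8.5.4, which allows an uncapped number of looks at P1 > 0.95 from 200 participants

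*SAP*

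**What the plan says.** - **Number of looks.** SAP 8.5.2 starts efficacy looks once at least 200 participants have reached Study Day 15. It gives the Bayesian approach as the reason, "so a strict interim analysis schedule is not prespecified", and leaves later looks to the DSMB. SAP 8.5.1 lets the DSMB ask for more, with no maximum. Protocol Section 7 promises frequent interim analyses and defers their timing and the stopping rules to the SAP.
- **Trigger.** SAP 8.5.4 sets P1 = P(OR > 1 | data) > 0.95, which covers "scenarios where an intervention arm would stop early for efficacy". The threshold does not change with the number of looks.
- **End of trial.** The only completion threshold in either document is 0.90. It appears in 8.5.4 for the predictive probability of success.
- **Error rate.** SAP 8.5.5 calls frequentist multiplicity control inappropriate for a Bayesian design. It then remarks that people often try to understand frequentist operating characteristics, and gives one sentence: 5% type I error and 86.4% power for OR 1.75 at 600. On repeated looks it concludes that "multiplicity adjustments are not warranted and would be inappropriate".
- **Sample size.** SAP Section 7 claims "90% power to detect an odds ratio of 1.75 or greater assuming a traditional proportional odds model and a type I error of 0.05" from "a sample size of 540 patients equally distributed among study arms".

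**The concern.** How often a rule declares benefit when OR = 1 is a property of the thresholds, the prior and the look schedule together. Section 8.5.5 offers a type I error tied to none of the three, and neither document gives a rate for the repeated P1 > 0.95 rule. Someone judging an early efficacy stop has only the 5% to go on. The DSMB, which chooses the schedule, cannot see what each added look costs.

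**Working it through.** **1. Reproduce the plan's own figure.** Whitehead's formula for 1:1 allocation is N = 12(z_α + z_β)² / [(ln OR)²(1 − Σp̄³)], where p̄ is the average of the two columns in the Section 7 table. Here 1 − Σp̄³ = 0.756 and ln 1.75 = 0.5596. With two-sided 0.05 and 90% power:

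N = 12 × (1.960 + 1.282)² / (0.3132 × 0.756) ≈ 532, or 267 per arm = 534.

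The stated 540 is reproduced to within about 1%, and 540/0.9 = 600. A one-sided 0.05 test would need only 434, so the 5% behind N is two-sided. A two-sided 5% leaves 2.5% in the direction of benefit. I compare with 5% below, which is the lenient choice.

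The same formula at 600 gives power Φ(√(600 × 0.756/12) × 0.5596 − 1.960) = Φ(1.48) = 93.1%, not 86.4%. Power at 600 also cannot be below the 90% stated for 540 under the same assumptions.

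**2. Put the Bayesian trigger on the z scale.**
- Prior (SAP 10.1): normal on ln OR with mean 0 and P(OR > 2) = 0.025. SD = ln 2/1.96 = 0.354; precision = 1/0.354² ≈ 8.0.
- Information at OR = 1 (an approximation using the Day 15 score only): I = n(1 − Σp³)/12 with the placebo column. 1 − Σp³ = 0.819, so I = 13.6, 27.3 and 40.9 at n = 200, 400 and 600.
- P1 > 0.95 is equivalent to Z > 1.645 × √(1 + 8.0/I).

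| n | Z needed | One-look crossing rate at OR = 1 |
|---|---|---|
| 200 | 2.07 | 1.9% |
| 400 | 1.87 | 3.1% |
| 600 | 1.80 | 3.6% |

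With 0.90 at n = 600 the cut-off is 1.282 × √(1 + 8.0/40.9) = 1.40, a one-look rate of 8.1%.

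**3. Repeat the looks.** Score statistics with independent increments were simulated at OR = 1. Any crossing counts as an efficacy claim. The schedules are assumptions, since the SAP fixes none. Interim looks use 0.95 throughout.

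| Looks | Final 0.95 | Ratio to one look | Final 0.90 | Ratio to one look |
|---|---|---|---|---|
| 600 only | 3.6% | 1 | 8.1% | 1 |
| two (400, 600 or 200, 600) | 4.9–5.1% | 1.4 | 8.8–9.0% | 1.1 |
| 200, 400, 600 | 6.1% | 1.7 | 9.6% | 1.2 |
| every 100 from 200 (5) | 7.2% | 2.0 | 10.3% | 1.3 |
| every 50 (9) | 8.3% | 2.3 | 10.9% | 1.4 |
| every 25 (17) | 9.1% | 2.5 | 11.5% | 1.4 |

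**4. Sensitivity.** The planned model uses Days 1 to 15, so its information may differ from that of one Day 15 score. Scaling I by 0.5 to 4 moves the five-look rate (final 0.95) from about 4.7% to 10.4%. Making the futility and harm stops binding changes the five-look rate little (about 7.1%).

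**The case against.** The strongest reply is that the SAP takes a deliberate and openly stated Bayesian position. A posterior probability can be read without adjusting for earlier looks, and 8.5.5 tells the reader that no adjustment is made and why. That stands, so the absence of an alpha correction is not the fault here. It does not answer the point, because 8.5.5 still quotes a type I error, and the crossing rate under OR = 1 changes with the looks whichever school one belongs to.

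Other parts of the reply also stand:
- The thresholds guide the DSMB and do not bind it, so counting each crossing as a stop gives an upper figure for the given schedule and information.
- The skeptical prior already lowers the rate. With a flat prior, five looks would give 11.7%.
- The Day 15 score only approximates the planned analysis.

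Three stronger readings are tempting, and the documents do not support them:
- *Repeated looks double the error.* A factor near two fits only some assumed schedules with 0.95 at the end. The ratio runs from 1.4 to 2.5 for two to 17 looks, and only from 1.1 to 1.4 with 0.90 at the end.
- *The SAP claims 5% for the sequential rule, or reports a one-look calculation.* It says neither. It does not explain how the 86.4% was obtained, and the one-look formula does not return it.
- *Stricter thresholds are required.* They would trade power for error, which is a design choice that nothing in the documents forces.

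**Conclusion.** The point holds as a gap between a quoted figure and the rule it accompanies. The 5% in 8.5.5 reflects no looks, prior or posterior threshold, while 8.5.2 and 8.5.4 allow an uncapped number of looks. On the Day 15 approximation, the quoted figure is exceeded with three or more looks if 0.95 applies throughout. It is exceeded even at a single look (about 8%) if 0.90 is the final criterion.

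No single rate can be assigned to this design, because the schedule, the final threshold and the information in the longitudinal model are all open. With half the information, for example, even five looks at 0.95 stay just under 5%. The documents settle that the rate is unstated and depends on the schedule. They do not settle its value.

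**What to change.** - **8.5.2:** list the planned efficacy looks or set a maximum, including any that the DSMB may request.
- **8.5.4:** state the success threshold at the final analysis, and whether the 0.90 used for predictive probability is that threshold.
- **8.5.5:** replace the 5% and 86.4% sentence with the simulated false-positive rate and power of the full rule (efficacy, harm and futility) under the planned longitudinal model and prior. Give them as a range over plausible schedules, at 540 as well as 600 evaluable participants. This also removes the conflict between 86.4% power at 600 and 90% at 540.

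The Bayesian thresholds can stay as they are. The cost is SAP wording and a short simulation, and the stated error rate will probably look less favourable than 5%. The change itself needs no extra patients.
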